Over the past decade, the use of computerized diaries to collect data in real time has supplanted paper and pencil methods as the gold standard for diary methodology. This is due to documented problems with paper and pencil methods - including the risk of participants' reporting on their behaviors cumulatively rather than in real time, or at the end of the reporting period. Additionally, ecological momentary assessment (EMA) minimizes missing data by providing automatic skip-outs and audible prompts, and allows for accurate reporting of missing data by reporting time of completion [35]. Adherence with these EMA methods is quite good, and appear to be highly dependent on training provided to participants (See Section 4.2 Intervention for the extensive training we provide to participants). In populations such as smokers, cancer patients, and pain patients using EMAs from three weeks to three months, adherence with "responding to auditory alerts," the most global measure of adherence, is in the range of 88-98% [35, 36].

In the current proposal given our short assessment time frame (14 days), the fact that we are examining an asymptomatic, non-clinical population, and the extensive training regarding how to use the interactive voice response (IVR) system that we offer, we believe that the study will be quite feasible with relatively low levels of nonresponse to audible prompts, and low levels of missing data overall. To achieve the high rates of adherence reported in the literature, we will follow the seven recommendations proposed by experts in the field of ecological momentary assessment [37]: 1) Integrate compliance concerns throughout the study protocol and build in compliance feedback and prompts for participants; 2) adequate training of subjects on the IVR; 3) make the IVR user-friendly; 4) program reminders into the IVR; 5) efficient handling within the IVR of question branching to administer correct questions in correct order; 6) built-in "livability" features to ease incorporation of IVR into their daily lives, and; 7) emphasize participant accountability for the data through tracking of adherence. We will evaluate reasons for refusal and patterns of missing data in primary statistical analyses. [name], an originator of EMA strategies and expert in methodological issues with EMA, has agreed to be a consultant on our study and will provide input during the EMA questionnaire development, implementation of the Phase II study, and data analysis.

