Health behavior theory may improve our understanding of the consistency of UVR protection. Witte's Extended Parallel Process Model [3] offers an account of the conditions under which illness threat may lead to health protective behavior. In the context of heightened illness threat (severity and susceptibility beliefs) and heightened beliefs that they can overcome the threat (self-efficacy and response-efficacy), people will act to do so via health protective behavior, or "danger control." In situations where threat is high but people don't believe they can manage it, behavioral avoidance, or "fear control" will result as people work to reduce their feelings of threat rather than their chances of becoming ill. Beliefs related to threat control include self-efficacy, or confidence that one can perform the behavior, and response-efficacy, or confidence that performing the behavior will protect against the health threat. Meta-analytic work examining this premise has found that pairing strong threat with high-self efficacy indeed maximizes behavior change [3]. In one of the only theories specifically addressing health behavior change maintenance, Rothman [50] has proposed and confirmed that satisfaction with the results of behavioral adoption - such as satisfaction with the results of smoking cessation or weight loss - determines whether individuals maintain health behavior over time [4, 5, 51].

We will examine these theory-based predictors - melanoma threat and efficacy, and satisfaction with UVR protection behavior - as between-subject and within-subject variables in this study. Accordingly, along with the most important decision factors, we will determine whether overall levels of these cognitive beliefs, or daily variations in these beliefs, are important in the maintenance of UVR protection over time in melanoma FDRs.

Study Significance. This is a measurement study aimed at understanding the discrete decision-making factors that dictate sun protection behavior on a daily basis. Given the clinical significance of even very few sunburn events, and the documented higher risk associated with some sun exposure contexts

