At each assessment session, they will be asked to respond to the question series using their telephone keypad. At approximately 12:30 pm they will be asked about their UVR protection and decision-making for the morning; and at approximately 5 pm, they will be prompted to complete this same assessment for the afternoon. At each time period after completing the IVR assessment, they will be prompted through the IVR system to record a brief (2-3 minute) description of their UVR protection strategies for that morning or afternoon. The IVR will allow a maximum of five minutes for the recording. The questions asking about sun protection use and decision making factors will follow a yes/no format to which they will respond using their telephone keypad. This format is a heavily-used, easy way to record health behaviors and decision-making factors consistent with EDTM. The IVR assessment survey will also include four closed-ended questions to assess: participants' perceived melanoma risk; perceived self-efficacy for following through with sun protection; beliefs about the effectiveness of sun protection in preventing melanoma; and level of satisfaction with decision to use/not use sun protection. Each assessment should require less than 10 minutes of the participants' time, keeping participant assessment burden low. Participants will have the option of being able to skip or refuse answering any questions they wish. Once the IVR has begun reading a question participants can interrupt the recording and move on by inputting their answer via the telephone keypad. The time at which participants complete the assessment will be electronically stamped on their assessment responses stored on the WEBCORE server. If the participant does not respond to the 1st call for each period (i.e., approximately 12:30 pm or approximately 5 pm), then the participant will automatically be called back up to 2 times within a one hour period. If the participant does not answer the 1st call for each period the system will leave the participant a voice mail message stating that they will be called back again shortly. If the participant does not answer the third follow-up call for a given time period the system will leave the participant a voice mail message stating that they will be called at the next assessment period. This same pattern will occur at the 5 pm assessment. Once the participant answers the call the IVR will not call again until the next assessment period. If the call is never answered, this assessment will not be able to be completed at a later time. However, the participant will be able to call the IVR system directly to complete the survey if they miss an outbound call for any assessment period.

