decision to engage in sun protection behavior this morning (or) this afternoon?" (1="Not at all satisfied," 2 for "a little satisfied," 3 for "moderately satisfied," 4 for "extremely satisfied.")

Within a week of completing the final IVR assessment on day 14, the study staff will call the participants to complete a brief program satisfaction survey consisting of 17 items to address any barriers to using the IVR. Additionally, in accordance with prior ecological momentary assessment research, the IVR will ask participants to self-report the extent to which the IVR prompting acted as a cue-to-action in their two-week assessment period of sun protection behavior. It is expected to take about 5 minutes to complete.

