9.0 PRIMARY OUTCOMES

The following ultraviolet radiation protection (UVR) behaviors will be assessed as primary outcomes:

- Continuous sun avoidance and/or shade-seeking behavior
- Sunscreen use
- Use of UVR protective clothing
- Use of hats

Our first aim is to generate models explaining decision-making about three UVR protection behaviors (sunscreen use, shade-seeking, use of protective clothing) in melanoma FDRs. We will model daily decision-making processes for UVR protection through qualitative and quantitative research strategies. In Phase I, we will conduct in-home ethnographic interviews with 25 melanoma FDRs and generate a decision making model for each UVR protection behavior for each melanoma FDR, and subsequently construct a composite decision-making model for each of the UVR protection outcomes (i.e., sunscreen use, shade-seeking, and UVR protective clothing use) representing prominent decision making factors across all 25 FDRs interviewed. In Phase II we will establish the validity of the models via examination of daily decision-making about UVR protection using ecological momentary assessment via IVR (over 14 days in the summer/early fall, at approximately 12:30 pm and 5 pm daily) in 60 different melanoma FDRs from Phase I. As outlined in EDTM methodology, we will report on the level of success of the decision-making model in predicting uptake of each of the three UVR protection strategies.

Our second aim is to examine theory-driven affective and cognitive predictors of UVR protection maintenance (sunscreen use, shade-seeking, hat use, and use of UVR protective clothing) assessed in real time. We will examine the role of melanoma threat and efficacy beliefs in determining UVR protection maintenance drawn from Witte's Extended Parallel Processing Model [3], and will examine the role of satisfaction in UVR protection maintenance drawn from Rothman's theory of health behavior maintenance

[4-6]. We will examine both between-person and within-person changes in these predictors, as well as salient decision-making factors (Identified in Aim I), in predicting maintenance of sunscreen use, shade-seeking, hat use, and use of UVR protective clothing.

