The general statistical paradigm for this Aim will be Generalized Estimating Equations (GEE) [83, 84] because of the repeated sampling of UVR protection behaviors and their predictors. Over a period of 14 days, each participant will generate a maximum of 28 assessments. Each assessment will yield 4 dichotomous outcome endpoints (sunscreen use, shade seeking, hat use and protective clothing). Additionally, each assessment will probe the decision factors, e.g., on environmental factors, convenience/situational factors, cognitive and social-interpersonal factors. For each outcome endpoint, we will fit a series of GEE models with a logit link. For example, we may fit the probability of sunscreen use as a function of weather (e.g., a dichotomous yes/no indicator of a sunny day). We will calculate the 95% confidence interval of the weather indicator on sunscreen use. The procedure will be repeated for other decision factors. We will use data visualization and graphs to summarize the 95% confidence intervals across decision factors, in the same exploratory procedures as outlined previously in O'Connor et al (2008).

Our exploratory GEEs approach is the most widely-used approach in the literature of intensive real-time data capture (aka Ecological Momentary Assessments, see Stone, 2009). Generally, these GEE models allow us to examine the extent to which each decision factor is associated with the health behaviors of interest. The repeated assessments will be clustered within persons. The working correlation structure will generally be fitted with an auto-regressive model because of the intensive daily assessments. The final number of covariates cannot be determined precisely at this time. However, care will be taken to minimize the number of confidence intervals to reduce concerns of multiple confidence intervals and to make the data more interpretable.

Power considerations.

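### The satisfaction item is described in two ways and Section 11.0 does not separate ratings given after use from ratings given after non-use, so its pooled coefficient does not test the maintenance theory

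*Combined protocol and SAP*

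**What the plan says.** - **Item wording.** Section 7.0 asks how satisfied the participant is with the "decision to engage in sun protection behavior this morning (or) this afternoon", on a four-point scale with no category for a period without protection.
- **Item description.** Section 4.2 (diary sampling procedure) lists the same item in the telephone survey as "level of satisfaction with decision to use/not use sun protection".
- **Theory.** Section 3.0 describes the maintenance theory as concerning "satisfaction with the results of behavioral adoption".
- **Role.** Under Aim II, Section 9.0 "will examine the role of satisfaction in UVR protection maintenance", and adds: "We will examine both between-person and within-person changes in these predictors".
- **Model.** Section 11.0: "For each outcome endpoint, we will fit a series of GEE models with a logit link". It states no lag, no restriction to periods with use and no satisfaction-by-use term.
- **Routing.** Section 3.0 promises "efficient handling within the IVR of question branching to administer correct questions in correct order" in general terms, but no branch is stated for this item. Section 4.2 adds: "Participants will have the option of being able to skip or refuse answering any questions they wish".
- **Non-use will occur.** Section 5.2 excludes only people who never use protection, and the power example in Section 11.0 assumes 60% to 70% sunscreen use.

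**The concern.** Satisfaction is a named Aim II predictor and the only measure of the maintenance theory. That theory speaks to people who have performed the behaviour and judge the result. A rating from a half-day without protection is a different quantity, whichever description of the item is correct:

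- On the Section 4.2 reading, the top of the scale means content to have protected from one person and content not to have protected from another.
- On the Section 7.0 reading, a non-user has nothing to rate and may score low or skip. The score, or the fact that it is missing, then carries information about use itself, which is the outcome.

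A single coefficient over all ratings mixes satisfaction with use status. Splitting the score into a person average and a deviation from it does not undo this, because both parts contain both kinds of rating. The study could report the theory as unsupported when it holds, or as supported when it does not.

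**Working it through.** **1. The plan's own figure.** Use of 70% against 60% gives an odds ratio (OR) of (0.7/0.3)/(0.6/0.4) = 1.56, matching the stated 1.55. A simulation with 60 people, 28 assessments, latent AR(1) correlation 0.10, 30% missed assessments, 5% then 5% attrition and two-sided alpha 0.01 gave power 0.78 for a person-level covariate with gradual attrition. Other 28-assessment variants at that correlation gave 0.75 to 0.83. The stated 78% is therefore reproduced, but it is for a generic predictor. The plan gives no figure for satisfaction.

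**2. Lagged pooled model (assumed form).** Let q be the share of rated half-days with use, p the base probability of use at the next assessment, and hu and hn the share of high scores after use and after non-use. Let b be the log odds ratio for repeating the last choice, c the carry-over of use in logits, L the inverse logit and a = logit(p). Then

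- P(next use | high) = [q·hu·L(a + c/2 + b/2) + (1−q)·hn·L(a − c/2 − b/2)] / [q·hu + (1−q)·hn]
- P(next use | low) = [q(1−hu)·L(a + c/2 − b/2) + (1−q)(1−hn)·L(a − c/2 + b/2)] / [q(1−hu) + (1−q)(1−hn)]

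The pooled OR is the ratio of the two odds. Only the 60% to 70% sunscreen use comes from the plan; every other input is assumed.

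*Worked case:* b = ln 2, p = q = 0.7, hu = hn = 0.5, c = 0. L(a + b/2) = 0.7674 and L(a − b/2) = 0.6226. High: 0.7 × 0.7674 + 0.3 × 0.6226 = 0.7240. Low: 0.7 × 0.6226 + 0.3 × 0.7674 = 0.6661. OR = (0.7240/0.2760)/(0.6661/0.3339) = 1.32.

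| True repeat-OR | Assumptions | Pooled OR |
|---|---|---|
| 2 | p = q = 50%, 60%, 70%, 80%; equal satisfaction; no carry-over | 1.00, 1.15, 1.32, 1.51 |
| 2 | p = q = 70%, equal satisfaction, c = 1 | 1.16 |
| 2 | p = q = 70%, hu 70%, hn 30%, c = 1 | 1.63 |
| 2 | the same, c = 2 | 2.10 |
| 2 | p = 70%; q = 80%, 90%, 95%, 99%; equal satisfaction; no carry-over | 1.51, 1.74, 1.86, 1.97 |
| 1 (none) | p = q = 70%, hu 70%, hn 30%, c = 1 | 1.44 |
| 1 (none) | p = q = 70%, hu 50%, hn 70%, c = 1 | 0.83 |

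*Check of the first no-effect row:* L(a + 0.5) = 0.7937 and L(a − 0.5) = 0.5860. High: (0.49 × 0.7937 + 0.09 × 0.5860)/0.58 = 0.7615. Low: (0.21 × 0.7937 + 0.21 × 0.5860)/0.42 = 0.6898. OR = 1.44.

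**3. Same-period pooled model.** If score and use come from the same call, the OR is odds(high | user)/odds(high | non-user). With 70% against 30% high it is (0.7/0.3)/(0.3/0.7) = 5.4. With 70% against 70% it is 1.0, and with 50% against 70% it is 0.43. This describes how ratings differ by use status and says nothing about maintenance.

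**The case against.** A reader might infer that a true satisfaction effect cancels in the pooled predictor. That is not a general result. Exact cancellation needs about 50% use, mirror-image slopes, equal satisfaction after use and non-use, and no carry-over. At the plan's 60% to 70% the same set-up dilutes the effect but leaves it positive, and other assumptions inflate it.

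Three further objections have weight.

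- **The item is global.** It lacks a referent only when none of the four methods was used, so the 70% sunscreen rate may understate the share of half-days with some protection. If each method were used independently in 50% of half-days, 1 − 0.5⁴ = 94% would involve some protection; at 70% each, 1 − 0.3⁴ = 99%. The distortion could then be small (1.97 for a true 2 at 99%). The plan gives no any-use rate, so this is possible but not shown.
- **The fielded survey cannot be checked.** Appendix C is listed but its content is not in the text available for review. That everyone is asked the item in the same words is an inference from Section 4.2, and the general branching commitment leaves room for routing. The two descriptions still conflict.
- **No lag is specified.** The table rests on an assumed lag-1 model with a two-level score. The same-period model, which fits the text equally well, fails in a different way and no better.

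The study also calls itself exploratory. That limits the weight of the point but does not make the coefficient interpretable.

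**Conclusion.** The point holds as one of interpretation. The two descriptions of the item conflict, no routing by use is stated, and the analysis does not separate ratings after use from ratings after non-use. The pooled satisfaction coefficient therefore does not test the theory set out in Section 3.0. It can be diluted, inflated or created without any true effect: illustratively 1.0 to 2.1 for a true repeat-OR of 2, and 0.83 to 1.44 for none. The direction and size depend on the any-use rate, the carry-over of use and how satisfaction differs by use, none of which the plan gives. The ranges are illustrations, not forecasts. The documents do not support the stronger statement that the effect cancels, nor the statement that high scores always mean opposite things; the latter follows only from the Section 4.2 reading. One Aim II predictor is affected, and the remedy needs no new data, so the change should be made.

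**What to change.** 1. Reconcile Sections 4.2 and 7.0 to one meaning of the item, matching what was fielded, and state who receives it and how a period without protection is answered.
2. In Section 11.0, test satisfaction in a lagged model. The score from one assessment predicts use at the next, with terms for any protection in the rated half-day and for its product with the score. Report the slope after use as the theory test and the slope after non-use separately.
3. For this global item, define use as at least one of the four methods. A method-by-method definition would treat an overall rating as specific to one method. In a same-period model, restricting to half-days when that method was used would make the outcome constant.
4. State that a same-period pooled coefficient will not be read as a satisfaction effect.

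**Cost.** This is a change of wording and analysis only, because use is recorded at the same call. The theory test rests on fewer pairs. Assuming lag-1 pairs and average retention of 97.5%, there are 60 × 27 × 0.7 × 0.7 × 0.975 = 774 pairs, of which 70%, or 542, follow use. With scores split evenly (271 per level), an OR of 1.55 centred on 70% use compares 74.4% with 65.2%. Power at two-sided 0.01 is then about 0.40, ignoring clustering. Treating 50%, 60% or 80% as both the share of pairs after use and the use rate gives about 0.33, 0.39 and 0.34. If nearly every pair followed some protection, with a 70% outcome rate, power would approach 0.58. All of these are below 78%, so the result should be reported as exploratory, with its confidence interval.

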8.0 TOXICITIES/SIDE EFFECTS

Individuals may find it stressful to answer questions regarding their sun protection behaviors. The risk associated with answering these questions is expected to be minimal. Participants' level of distress will be carefully monitored by the research staff and by [name]. Participants may refuse any part of their participation, from answering questions that they find distressing, to refusing the home tour, or recording twice-daily audio narrative diaries through the IVR system. If a participant is significantly distressed, [name] or a covering attending will assess the participant and make an appropriate referral for clinical care if needed.

9.0 PRIMARY OUTCOMES

The following ultraviolet radiation protection (UVR) behaviors will be assessed as primary outcomes:

- Continuous sun avoidance and/or shade-seeking behavior
- Sunscreen use
- Use of UVR protective clothing
- Use of hats

Our first aim is to generate models explaining decision-making about three UVR protection behaviors (sunscreen use, shade-seeking, use of protective clothing) in melanoma FDRs. We will model daily decision-making processes for UVR protection through qualitative and quantitative research strategies. In Phase I, we will conduct in-home ethnographic interviews with 25 melanoma FDRs and generate a decision making model for each UVR protection behavior for each melanoma FDR, and subsequently construct a composite decision-making model for each of the UVR protection outcomes (i.e., sunscreen use, shade-seeking, and UVR protective clothing use) representing prominent decision making factors across all 25 FDRs interviewed. In Phase II we will establish the validity of the models via examination of daily decision-making about UVR protection using ecological momentary assessment via IVR (over 14 days in the summer/early fall, at approximately 12:30 pm and 5 pm daily) in 60 different melanoma FDRs from Phase I. As outlined in EDTM methodology, we will report on the level of success of the decision-making model in predicting uptake of each of the three UVR protection strategies.

Our second aim is to examine theory-driven affective and cognitive predictors of UVR protection maintenance (sunscreen use, shade-seeking, hat use, and use of UVR protective clothing) assessed in real time. We will examine the role of melanoma threat and efficacy beliefs in determining UVR protection maintenance drawn from Witte's Extended Parallel Processing Model [3], and will examine the role of satisfaction in UVR protection maintenance drawn from Rothman's theory of health behavior maintenance

[4-6]. We will examine both between-person and within-person changes in these predictors, as well as salient decision-making factors (Identified in Aim I), in predicting maintenance of sunscreen use, shade-seeking, hat use, and use of UVR protective clothing.

